The videos will be stored in keeping with the strict UK data protection laws and kept on a secure UCL IDHS (data safe haven) server which conforms to the NHS information governance toolkit. As inter- and intrarater reliability testing will involve NHS Staff as subjects, a detailed application for these assessments has been made to the UCL Research Ethics Committee, The inter- and intrarater reliability testing of the RHS in a UK cohort of neuromuscular physiotherapists will form part of an Advanced Physiotherapy MSc project conducted by the SMA REACH physiotherapist.

There will be specific forms for medical practitioners and physiotherapists. Recording of the information will involve use of the SMAREACH scannable key medical information and medical assessment forms for the medical assessment/physical examination. Regarding the physiotherapy assessment a newly created SMA REACH UK worksheet has been created.

Information from both assessments will be uploaded to the anonymised SMA REACH UK database. Patients will be identified by an anonymised SMA REACH UK code, the master key information will be available to specific members of the research team and the clinic administrator. In the initial stages this will involve the use of the previous SMArtnet system and where the SMArtnet system does not allow for the recording of new outcome measures a separate database for novel outcomes will be kept. Following the initial pilot of outcomes the SMA REACH UK database will then be created and all anonymised assessment information will be stored here.

Figure 2. Current Schedule of events for SMA REACH UK

Anticipated Milestones	Anticipated target date	
Open SMA sites across the UK and recruit eligible patients to SMA-REACH	Ongoing	
National SMA-REACH meeting	Annually	
Piloting standardised physio assessment database for SMA patients	Ongoing	
Continue recruitment at GOSH (expected to recruit 2-4 patients per month) and Newcastle (expected to recruit 1 patient per month)	Ongoing	
Establish a merged database with clinical and genetic data		
Organize a patient/parent focus group with clinicians aimed to update on standards of care and implications of potential upcoming therapies; dissemination of results.	Annually or as required	
Workshop and training for other UK centres in preparation for expansion of the Network to other UK centres	Annually	
Recruit Adult SMA patients by opening adult centres to SMA-REACH	Start 2019	
Allow the stabilization of the ISMAC collaboration with Biogen. Collect and send data to Biogen upon patient consent Allow the prospective long-term follow up of patients with SMA to obtain information about both the natural history of the disease and the effect of different SMA specific drug treatments	Ongoing	
Continue with recruitment/data collection and publication of data	Ongoing	

Visits to sites

There will be regular sponsor led monitoring visits to sites open to SMA-REACH, as part of audits and reviews.

Discussion of the Results.

The participating centres will meet before starting recruitment and one year after the recruitment has started to discuss the state of recruitment and to plan further steps. A final meeting will be held after the results of the statistical analysis will be available.

Further Statistical Design/Analysis.

The distribution of each of the outcome variables will be assessed. Appropriate descriptive statistics (means and standard deviations for normally distributed data, medians and ranges for data not normally distributed) of each of the measures at each time point will be compared. Also, the mean and standard deviation of change from baseline to 6 months and 1 year will be calculated for each measure. The sample size should provide sufficient precision in the estimates of the means and standard deviations.

Descriptive analysis will be carried out by computing means and medians of continuous variables (as appropriate according to the type of distribution, i.e. whether approximately normal or not), together with ranges, standard deviation and standard errors. Proportions and 95% confidence intervals will be computed for categorical variables.

The Cronbach's alpha will be used to assess the internal consistency of each test. The inter- and intra-rater reliability will be evaluated through the Intraclass Correlation Coefficient (ICC).

Appropriate statistics for repeated measures study design (ANOVA and multivariable mixed effects regression modelling) will be used to assess changes of scores in each scale over time (baseline, 6 and 12 months).

More in-depth examination of scale robustness will be performed via RASCH analysis.

The data elicited from the patient interview will be analysed with qualitative methods according with the specific purpose of the set of interviews.

Confidentiality of Personal Data

Personal data which will be stored for routine clinical purposes will only be accessible to authorized individuals in this study. Personal data will not be entered into the database as part of this research. The clinical data collected will only be linked to the patient by a study code number and will contain no personal identifiers. Informed consent/assent will be obtained from participants to collect and retain this data. The data that will be used for analysis and dissemination for research purposes will be completely anonymised. All staff in UK NHS Trusts are obliged to adhere to their Duty of Confidentiality, GDPR and Caldicott Principles.

Potential Risks to Participants and Researchers

There are no extra invasive procedures involved in this research protocol. Assessments will be designed to minimize fatigue for individuals and hospital attendance. Additional assessments as part of the ISMAC collaboration are not expected to impact on patients' and family's clinical commitment as these will coincide with their clinical appointments.

Potential Benefits for Participants

The information collected in the database will lead to a better monitoring of current standards of care and improving where needed. Furthermore this may facilitate future patient recruitment in clinical trials.

Participants will not receive any payments specifically for taking part in this study. We expect to conduct the assessment in coincidence with the clinical appointment (every 7 months +/- 1 month), however due to the slightly extended time needed for the assessment, refreshments for patients will be provided. It is unlikely the assessments will fall outside the clinical appointment but whenever this will occur, travel costs or reimbursements will be available for families.

Ethical Issues

No specific issues have been identified to arise from this study. Informed consent/assent will be documented using the information sheet and consent/assent form, and GDPR will be adhered to as per routine clinical care. All data held and disseminated for research purposes will be anonymised, containing no personal identifiers.

The study protocol and associated documents for use in the study will be reviewed and approved by the Research Ethics Committee. The commencement of the study at each UK site will be subject to NHS R&D management approval.

Safety Monitoring plan

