Inclusion criteria:

All patients with genetically confirmed SMA type 0, I, II and III aged from neonates to adult age will be recruited (adults can be recruited). The diagnosis of SMA must be documented by the absence of SMN1 on standard genetic tests for the disorder, and the determination of type I, II and III SMA by the ability to maintain a sitting position when placed, and if they are ambulant/non-ambulant. When possible, each patient should also have the determination of the SMN2 copy number.

Exclusion criteria

There are no exclusion criteria if a genetic diagnosis of SMA has been confirmed.

Involvement in clinical trials is not an exclusion criterion nor having had surgical procedures. Patients who are participating in clinical trials with novel treatments will also be included in the database although the data from this subgroup won't be analysed in the natural history study, nor shared with pharmaceutical companies and other third parties as part of the ISMAC collaboration. Patients who have had orthopaedic surgery will also be eligible, as this will further inform the natural history of the condition after surgery. Participants currently or previously taking a treatment intended to effect change in SMA (i.e. salbutamol, hydroxyurea, valrpoic acid, carnitine, etc) will also be included in the study as no effective treatment has been identified to date. The use of concurrent medications will be recorded at each visit.

Patient selection criteria/Number of patients/Methods for identifying and recruiting patients

Patients will be selected amongst those attending standard follow up clinics in the participating centres according to the mentioned inclusion criteria. We do not foresee many difficulties in recruiting patients as the project does not require any extra appointments for the patients and their families and the assessment does not require any extra invasive procedure on top of the standard clinical procedures. It does, however, include an extended physiotherapy assessment.

We anticipate that we will be able to enrol the vast majority of the patients regularly followed in the routine clinical care. . **Medical Assessment/Physical Examination**

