Standard clinical procedures for all patients will include the recording of the following parameters at each visit (every 7 months +/- 4 weeks) (Consensus Statement for Standard of Care in Spinal Muscular Atrophy, Ching H. Wang, et al, Journal of Child Neurology Volume 22 Number 8 August 2007 1027-1049), in addition to the procedures outlined in appendix 3

Height (standing or arm-span), weight and blood pressure

Physical examination as noted in appendix 3

Pulmonary function test (Spirometry) will be also performed at each visit (forced expiratory vital capacity, FVC as percent predicted). No additional tests are required.

In young children (<5 years) or when there is no compliance, or following clinical indication (daytime hypercapnia or FVC<60% at the spirometry), regular overnight sleep studies might be indicated as part of the current standard of care. No additional tests are required.

ECGs are usually performed at the first appointment and repeated every few years as follow-up or more often if there is a clinical indication.

Additional ECG will be performed prior commencing Salbutamol therapy and after three months of being on therapy. Follow-up ECGs are performed once a year in all patients receiving salbutamol therapy.

Bloods are taken on average once a year to monitor the Vitamin D level and electrolytes in patients on Salbutamol. No additional bloods are required.

Whole spine X-ray will be performed following the clinical indication (i.e. presence of spinal curve, back pain) and repeated follow-up will depend on the scoliosis progression. No further tests other than what is required for clinical care will be requested.

Lumbar spine or total body DEXA scan are not regularly performed and are requested following a clinical indication (bones fractures following minimal trauma, back pain, low vitamin D level, pre-op for spinal surgery). No additional DEXA scans other than those required as part of routine clinical care are required as part of this project.

Speech and language therapy and dietician review will be recorded when requested following a clinical indication.

Please refer to appendix 3 for additional standards of care parameters

Furthermore, we will record any patient's cause of death, and number of chest infections within the last 6 months.

Physiotherapy Assessment

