c. Piloting standardized assessment database for SMA patients to characterize the course of SMA patients and to report data on clinical and biological outcomes for use in trial planning. We will make use of the SMArtnet and SMA Registry infrastructure to create a data house where these measures can be assessed, housed and added to.

d. Patients with genetically confirmed SMA followed at all neuromuscular centres seeing SMA patients, will be consented to be recruited into a longitudinal natural history study and sample size will be based on the figures determined from the point a. (identify and describe SMA patients population seen at GOSH and Newcastle). The recruitment period will be ongoing with the planned full assessment (clinical and physiotherapy) will be performed at baseline, 6 months and 12 months (for most of the patients these latter assessment will fall in to the second year). In parallel to these first UK sites, other international centres with high expertise in SMA care and clinical trials will run parallel projects also recruiting SMA patients to piloting the new tools during their physiotherapy assessment. The principal sites, including the international sites running parallel projects, will meet before the recruitment begins at each site to discuss practical issues and to perform training sessions and inter-observer reliability studies among all the examiners involved. Before starting the recruitment, a designed External Advisory Board will be consulted on the aims of the project and will be invited to attend the Focus group. e. As described above in the physiotherapy assessment section, various physiotherapy assessment tools will be will be piloted during an extended physiotherapy assessment. The SMA REACH UK study will run alongside parallel projects in Italy and USA which will use the same outcome measures, giving a larger dataset which will allow for more rigorous Rasch and psychometric analysis in order to develop robust outcome measures to assess the physical abilities of patients with SMA, thus ensuring the UK is clinical trial ready and aligned to the international agenda.

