f. The first focus group will be hosted by GOSH and UCL Institute of Child Health and will occur with the funding and organizational assistance of the well-known UK SMA charities, As discussed in past SMA conferences, the patient population is eagerly awaiting clinical trials. There is a need to identify what study parameters the patient population find feasible and acceptable. This focus group will be focused to identify the degree to which each outcome measure is tolerated, the acceptable frequency of visits, the duration of each visit and length of the study, as well as the general feelings towards study design (i.e. is a traditional 1:1 placebo: active study design acceptable or should alternative study methodology be considered). This information will be collected and analysed after the focus group and will serve as advice for clinical trials, with the attempt to tailor study design to meet patient/family needs and expectations.

Phase 2 Objectives:

- a. longitudinal data analysis collected as required to monitor standard of care and change if needed
- b. organise workshops and training in preparation to expand the Network to the remaining UK Centres

The first longitudinal data analyses will be performed once all recruited patients will have completed at least six months in the study. We will establish the distribution of scores and variability observed over the period from the started recruitment. At this stage the final database amendments will be completed before the network is expanded to national level and remaining centres will be invited to participate to the standardized collection of data. The sites involved will meet before the recruitment is expanded to discuss practical issues and to perform training sessions and inter-observer reliability studies among all the examiners involved.

This second phase will include the provisions of national network workshop and training, equipment and consumables.

This project is expected to be extended further to allow the following objectives:

- a. Initiation and maintenance of the broader network
- b. Periodic longitudinal data analysis collected
- c. Organize patient/parent focus groups with clinicians aimed to discuss implications of potential upcoming therapies; dissemination of results.
- d. Allow the stabilization of the ISMAC collaboration

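### Clinic visits every 7 months do not supply the 6- and 12-month assessments that the study design plans and the analysis reports

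*Protocol*

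**What the plan says.** The protocol describes the timing of follow-up in two ways.

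**A 7-month cycle.**
- Medical Assessment/Physical Examination records the standard parameters for all patients "at each visit (every 7 months +/- 4 weeks".
- Potential Benefits for Participants extends this to the study assessment: "We expect to conduct the assessment in coincidence with the clinical appointment (every 7 months +/- 1 month".
- The patient selection section explains why the two coincide: "the project does not require any extra appointments for the patients and their families".

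**A 6- and 12-month schedule.**
- Study design, Phase 1, item d states that the full clinical and physiotherapy assessment "will be performed at baseline, 6 months and 12 months".
- Further Statistical Design/Analysis states that "the mean and standard deviation of change from baseline to 6 months and 1 year will be calculated for each measure". It then names repeated-measures ANOVA and mixed effects regression for scale scores at baseline, 6 and 12 months.
- The optional strength and function sub-study, with 5-10 patients, also describes routine clinics as six-monthly.

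The protocol does not rank the two schedules, and it gives no rule for assigning a 7- or 14-month visit to a 6- or 12-month time point.

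**The concern.** A site that follows the 7-month cycle produces no regular data at 6 or 12 months, yet those are the two points at which change is to be summarised. Someone has to decide whether a 7-month visit counts as the 6-month result. If it does, the mean change carries a label shorter than the time over which it accrued.

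This matters because Phase 1, item c intends the database "to report data on clinical and biological outcomes for use in trial planning". A mean and standard deviation of change are typical inputs to the design of a later trial, and their reader needs to know the interval they cover. No confirmatory test in this study depends on them.

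**Working it through.** The protocol states no figure to reproduce, so the check is calendar arithmetic followed by a conditional estimate of size.

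**Inputs from the protocol.** Interval 7 months. Window 4 weeks (Medical Assessment/Physical Examination) or 1 month (Potential Benefits for Participants). Analysis points 6 and 12 months.

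**Convention.** 1 month = 30.4375 days, so 4 weeks = 28/30.4375 = 0.92 month.

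**Do the windows reach 6 and 12 months?** The first follow-up is 7 ± w. The second is 14 ± w if counted from baseline, or 14 ± 2w if counted from visit to visit.

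| Window | First follow-up (months) | Second, from baseline | Second, visit to visit |
|---|---|---|---|
| ± 4 weeks | 6.08 to 7.92 | 13.08 to 14.92 | 12.16 to 15.84 |
| ± 1 month | 6 to 8 | 13 to 15 | 12 to 16 |

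With the 4-week window, 6 months lies just outside and 12 months lies outside on either counting. With the 1-month window, 6 months is the earliest permitted edge. Twelve months is then reached only on visit-to-visit counting, and only if both visits fall at their earliest limit.

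**Size, if visits follow the 7-month cycle and are labelled 6 and 12 months.** Under linear change the overstatement is t/6 − 1 at the first follow-up and t/12 − 1 at the second.
- At exactly 7 and 14 months: 7/6 − 1 = 14/12 − 1 = 16.7%.
- At the edges of the 1-month window, first follow-up: 6/6 − 1 = 0% to 8/6 − 1 = 33%. Second follow-up, visit to visit: 12/12 − 1 = 0% to 16/12 − 1 = 33%.
- At the edges of the 4-week window, first follow-up: 1.3% to 32%.

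**If decline slows.** The Introduction describes an early, faster loss followed by a plateau or slow decline. Take change(t) = A(1 − 2^(−t/h)), where the half-life h is an assumption.

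| h (months) | 7 against 6 months | 14 against 12 months |
|---|---|---|
| 6 | +10.9% | +6.9% |
| 12 | +13.5% | +10.9% |
| 24 | +15.0% | +13.5% |

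**In scale points.** The protocol gives no rate of change. At an assumed d points per year, the excess is d/12 at the first follow-up (one extra month) and d/6 at the second (two extra months). For d = 0 to 3, that is 0 to 0.25 and 0 to 0.5 points. The HFMSE and RHS have maxima of 66 and 69.

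**The case against.** **Scope.** The 7-month interval in Medical Assessment/Physical Examination covers clinical procedures, whereas the repeated-measures analysis concerns scale scores from the physiotherapy assessment. The physiotherapy section sets no interval of its own. On this view, item d is the only explicit schedule for the full assessment, it agrees with the analysis section, and the 7-month figure merely describes routine clinics. It is true that no bias arises if item d governs. But Potential Benefits for Participants places the study assessment at the 7-month appointment, so the conflict does reach the scales.

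**Flexibility.** That section speaks of an expectation and offers travel costs for assessments held outside clinic. It also calls such assessments unlikely, so they cannot be the regular source of 6- and 12-month data.

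**Analysis detail.** Using actual dates in a mixed model is commonly settled in a statistical analysis plan, which is not at hand here. This stands as far as model specification goes. The visit schedule is protocol content, however, and the change scores are tied to 6 months and 1 year in the protocol itself.

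**The analysis trigger.** A reader might infer a second defect from the Phase 2 statement: "The first longitudinal data analyses will be performed once all recruited patients will have completed at least six months in the study". A patient with exactly six months in the study would normally have only a baseline assessment under the 7-month cycle. The text does not support treating this as a separate fault. Six months is a minimum for the latest recruit, and the protocol does not require a follow-up from every patient at that analysis. Figure 2 plans to "Continue recruitment at GOSH (expected to recruit 2-4 patients per month) and Newcastle (expected to recruit 1 patient per month", which is 3 to 5 a month. If recruitment ran up to the cut-off, (7 − 6) × 3 to (7 − 6) × 5 = 3 to 5 late recruits at those two sites would lack a follow-up, or 0 to 10 across the windows. The study anticipates 400-600 patients overall. This is an alignment point only.

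**Conclusion.** The contradiction in the text is certain: two assessment schedules are stated, their windows do not reconcile them, and neither is given precedence. The consequence is modest, and the severity is minor.

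The 17% figure holds only if clinics keep to the 7-month cycle, visits are labelled 6 and 12 months, and change is linear. Under linear change the range is 0% to 33% across the windows. Under the assumed slowing decline, with visits at exactly 7 and 14 months, it is about 7% to 15%. It is zero if item d governs. At the assumed rates, visits at exactly 7 and 14 months add at most half a scale point, which is negligible in a near-stable cohort.

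A reader might infer that the study's change estimates will be biased by 17%. The protocol does not support that. It does not say visits will be relabelled, and the mixed effects model it names can use actual dates. Only descriptive estimates are exposed.

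**What to change.** Keep the 7-month clinic cycle and state it with one window in Medical Assessment/Physical Examination, in Study design Phase 1 item d, and in Potential Benefits for Participants. This adds no patient visits. As tidying, bring the sub-study's clinic interval and the Phase 2 trigger into line.

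Amend Further Statistical Design/Analysis so that the planned mixed effects model uses actual time since baseline and gives change at 6 and 12 months as model-based estimates.

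The cost is protocol wording, use of the assessment dates and slightly more analysis work. If the Phase 2 trigger is moved to the close of the first follow-up window, at about 8 months, the first longitudinal analysis comes about 2 months later.

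If the sponsor prefers 6-month visits, the protocol should say that this means 12/6 = 2.0 visits a year rather than 12/7 = 1.7, and should revise its statement that no extra appointments are needed.

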All patients regardless of SMA type or ambulation status will receive a physiotherapy assessment in keeping with standard clinical practice for children and young people with SMA. This will involve gathering a thorough physiotherapy subjective history (current concerns/changes regarding mobility, falls, fatigability, endurance/exercise tolerance, equipment and orthotics evaluation, discussion of orthopaedic concerns, pain, activities of daily living, environmental concerns and home modifications); and an objective assessment of motor development, muscle length/contractures, joint range of movement, muscle strength (myometry or manual muscle testing if appropriate) and posture involving spine, head, lower and upper limbs. For the ambulant population further assessment of higher level motor functions such as gait, standing posture, stairs, 10 metres run/walk test etc. will be part of the assessment.

In addition to the standard physiotherapy assessment, several functional measures will be used to assess current level of physical functioning. Due to the nature of this project and the current work being done in developing more sensitive SMA specific scales it is likely that that the protocol will be drawn from but not exclusively involve the scales mentioned below. Novel outcome measures may also be trialled and form part of the protocol.

Functional Scales for Non-Ambulant Patients

SMA Type 1

Due to the nature of this form of SMA and the young age of the child usually one of the below assessments will be completed, only in exceptional circumstances both will be completed. Length of time to complete these assessments will vary, but can be estimated to take 30 minutes.

CHOP INTEND (The Children's Hospital of Philadelphia Infant Test of Neuromuscular **Disorders**) – this is a scale used for the assessment of movement and function of very weak infants with SMA type 1 or weak SMA 2. It consists of 16 items of motor function graded 0-4 with a maximum achievable score of 64 (Glanzman et al, 2010). We estimate this will take 30-40 mins per patient.

WHO DEVELOPMENTAL MILESTONES- For SMA Type 2/3 non-ambulant (all SMA patients). – either conducted as a stand-alone assessment od part of the RHS scale – see below)

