Egan Klassification Scale (EK2) – This will be used for older non-ambulant patients and consist of a series of 17 questions reporting on physical function including ability to transfer, cough, swallowing, fatigue and arm function. The EK measure has been determined to be valid for use in non-ambulatory individuals with SMA (http://rcfm.dk/english/ek-scale/#english-versions-and-manual)

It will take approximately 5 minutes to complete the EK2. Additional PROMs will need to be reviewed for length of time they take to be completed.

Additional physiotherapy assessments (as required):

HINE Section 2 (non-sitter infants) – includes 8 items scored on a 5-point scale with 0 as the absence of activity, and a maximum score of 4 points

WHO Motor Milestones (all patients)- includes 6 gross motor milestones as defined by WHO. These milestones are included within the RHS assessment and will be conducted in addition to the CHOP-INTEND where applicable.

Vignos scale (all patients)- to assess lower extremity function. Grading ranges from 1-10; 1 means that the subject can walk and climb stairs without assistance and grade 10 refers to the subject being confined to a bed

Brooke scale (all patients)- to assess the upper extremity function. Grading ranges from 1-6; 1 means that the subject can elevate their arms full range to the head with the arms straight and while grade 6 refers to no useful function of hands. This is the entry item on the RULM.

Impact of Range of Motion (ROM) on Function and manual strength testing

ROM and strength testing will be recorded according to clinical relevance. Grading should be assigned as follows:

- None = no contracture
- Minimal = no influence on function
- Moderate = Some impact on function but still able
- Severe = Significant impact / makes function difficult or impossible

Please refer to appendix 1 for detailed procedures.

Collection of retrospective data and ethnicity

As part of the study, we will collect retrospective data going back over 10 years (collected on the SMARTNET database) in order to ensure all clinical data is captured. Furthermore, we will collect information on each patient's ethnicity.

Patient Interviews (OPTIONAL):

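### Joint range and strength are assessed in every patient but recorded by an undefined clinical relevance, so a blank cannot be interpreted and missing values may depend on the finding and the centre

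*Protocol*

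**What the plan says.** The protocol's Physiotherapy Assessment section states that "All patients regardless of SMA type or ambulation status will receive a physiotherapy assessment". That assessment includes "an objective assessment of motor development, muscle length/contractures, joint range of movement, muscle strength". Myometry and manual muscle testing, the methods for strength, are qualified there as applying where appropriate. Joint range and contractures carry no such qualifier.

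The block headed Impact of Range of Motion (ROM) on Function and manual strength testing follows the list of additional assessments done as required. Its recording rule is "ROM and strength testing will be recorded according to clinical relevance". It then gives four grades, None, Minimal, Moderate and Severe, the first defined as "None = no contracture". In the list just above, the WHO milestones, Vignos and Brooke scales are each marked for all patients, and the HINE for non-sitting infants. ROM and strength have no such label, only the relevance condition. Detailed procedures are referred to Appendix I.

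The section on approximate length of assessment includes joint range for infants and for non-ambulant type 2 and 3 patients. Its ambulant line does not.

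Further Statistical Design/Analysis says "Proportions and 95% confidence intervals will be computed for categorical variables". It also plans change from baseline to 6 months and 1 year for each measure.

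**The concern.** Assessment is universal while recording is discretionary. No criterion for relevance is given, and the protocol text has no code for not tested or not relevant. If clinicians tend to enter a joint when it is a problem and pass over it when it is not, the recorded values are enriched for abnormal findings, and a proportion computed from them is too high.

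The project's purpose is harmonised longitudinal data from up to 20 UK centres, used for natural history and for the effect of SMA drug treatments. If centres judge relevance differently, a difference between them in recorded contracture may reflect recording habits. A patient whose early normal findings were not entered has no baseline grade, and the first recorded grade may come after onset. An analysis plan can state how blanks are handled, but it cannot recover findings that were made and never written down.

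**Working it through.** **Plan's own figure.** There is none to reproduce. The protocol states no contracture prevalence and no recording rate, so every value below is an assumption.

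**Formula.** Let p be the true prevalence of contracture among those assessed, r1 the share of abnormal findings recorded and r0 the share of normal findings recorded. The proportion among recorded values is

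p·r1 / (p·r1 + (1 − p)·r0).

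It equals p when r1 = r0, exceeds p when r1 > r0 and falls below p when r1 < r0.

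**Contracture, all abnormal findings recorded (r1 = 1).**

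| True p | r0 = 0.8 | r0 = 0.5 | r0 = 0.2 |
|---|---|---|---|
| 40% | 0.40/(0.40 + 0.48) = 45% | 0.40/(0.40 + 0.30) = 57% | 0.40/(0.40 + 0.12) = 77% |
| 20% | 0.20/(0.20 + 0.64) = 24% | 0.20/(0.20 + 0.40) = 33% | 0.20/(0.20 + 0.16) = 56% |

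**What analysis could recover.** Suppose the number assessed is known but a blank may mean anything. With p = 40% and r1 = 1, the blanks are (1 − r0) × 0.60 of patients: 12%, 30% and 48% for r0 = 0.8, 0.5 and 0.2. Counting all blanks as normal, then all as abnormal, bounds the prevalence at 40–52%, 40–70% and 40–88%. Only a rule on what a blank means would narrow these bounds.

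**Onset and change.** A new contracture can be placed between two visits only if None was entered at the visit before. Under this model that happens for a share r0 of new cases: 80%, 50% or 20%. Likewise a share r0 of patients unaffected at baseline have a baseline grade. Both uses are weakened, and they are lost entirely only at r0 = 0.

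**Strength.** The direction can reverse. If testing is left out in patients too weak or too young, so that r1 = 0.5 and r0 = 1, a true 50% appears as 0.25/(0.25 + 0.50) = 33%. With r1 = 1 and r0 = 0.5 the same 50% appears as 0.50/(0.50 + 0.25) = 67%. The protocol does not say which applies, and no grade in the scale is worded for strength.

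**Complete entry.** With r1 = r0 = 1 the formula returns p for any p.

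**The case against.** A reader might infer that the protocol orders recording only when a finding is abnormal, and that contracture and weakness are therefore overstated. The text does not say this. It makes recording depend on relevance, and a scale that begins with None shows that normal joint range was meant to be enterable. Loss of normal findings is a risk that the rule allows, not a rule in itself.

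Relevance might instead select joints, muscles or patient groups, with everything selected then graded from None to Severe. The absence of joint range from the ambulant line fits this, and missing values would then follow patient group and not result. This reading cannot be excluded, but two things weaken it. The ambulant line is a time estimate and also leaves out the upper limb module and WHO milestones, which the section on ambulant scales includes, so it looks abbreviated. And the neighbouring list names patient groups explicitly where it means them.

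The manuals and worksheets under Appendix I are not shown and may require complete entry or provide a not-tested code. If so, the practical damage is smaller, but the protocol sentence would still permit blanks and would conflict with the worksheet.

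The statistical section's sentence on proportions is general. It names neither ROM nor contracture and fixes no denominator, and a denominator may properly be left to an analysis plan. That stands. The fault lies in the recording rule.

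It would also go too far to say that onset cannot be dated, or that change from baseline exists only for patients already affected. Both require that no normal finding is ever entered.

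**Conclusion.** The point holds as a conflict within the protocol and a badly fixed recording rule. Contractures, joint range and strength are assessed in everyone, recording is left to an undefined judgement, and a blank has no stated meaning. Missing values may therefore depend on the finding and on the centre.

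For contracture the likely direction is overstatement, provided that normal findings are entered less often than abnormal ones. The size cannot be derived from the documents; the 45% to 77% for a true 40% illustrates the mechanism and is not an estimate. For strength the documents do not support a claim that weakness is overstated, and the direction is unknown. Dating of onset and change from baseline are at risk but not ruled out.

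The conclusion rests on the protocol text alone, since the Appendix I worksheets were not available. The change is worth making because findings that were never entered cannot be reliably recovered later.

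**What to change.** Replace the recording sentence in the ROM and strength block with wording such as: *For each joint on the worksheet, the ROM grade (None, Minimal, Moderate, Severe) is recorded for every patient at every full physiotherapy assessment, including None. Strength is recorded wherever it was tested. Otherwise, not tested and the reason are entered.* The rule works joint by joint because a single grade per patient would leave blanks for individual limbs unexplained.

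Compute proportions over all patients assessed and report the number not tested beside them. Bring the ambulant line in the section on length of assessment into agreement with the Physiotherapy Assessment section, and check that the Appendix I worksheets carry the same fields and codes.

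The cost is a few extra entries per visit for findings that the protocol already has examined. No procedure is added and clinical care does not change.
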